#### **9.2.1.4 Vital signs and physical exam**

A complete physical exam (including sitting blood pressure and heart rate, temperature and respiratory rate) will be performed at Visit 1 (Screening) and Visit 9 (Week 26); abbreviated physical exams (including sitting blood pressure and heart rate) will be performed at all other on-site visits. The abbreviated physical exam should focus on cardiac and respiratory systems, as well as any areas important for assessment of AEs if necessary. Three separate seated BP and heart rate measurements should be taken with at least 1 minute between measurements following a 5-minute rest period, and prior to phlebotomy. Full details and directions for the measurement of blood pressure are presented in [Appendix D](#).

#### **9.2.1.5 Electrocardiogram variables**

The ECG assessment of “normal” or “abnormal” will be analyzed.

A 12-lead ECG record is performed locally at Screening (Visit 1), Baseline (Visit 3) and Week 26 (Visit 9).

The 12-lead ECG should be performed after at least 10 minutes in supine position and prior to the morning IMP administration. The Investigator should review the ECG and document the interpretation, sign and date it on the ECG print out and report it in the e-CRF. Each ECG trace is analyzed in comparison with the screening recorded trace. All original traces are kept as source data.

Note: Any new ECG abnormality should be rechecked for confirmation and reported as appropriate for that finding.

#### **9.2.1.6 Self-monitoring of blood glucose**

A meter for self-assessment of blood glucose will be dispensed at the Run-in visit (Visit 2). In addition to home measurements of self-monitored blood glucose, self-monitoring of blood glucose will be performed at Run-in (Visit 2) and all subsequent on-site visits. Glucose meters used for SMBG display results as plasma glucose concentration.

Patients will also receive a patient diary at all on-site visits from Visit 1 to Visit 9. The diary will be reviewed at all on-site visits from Visit 2 to Visit 10. Self-assessed blood glucose levels will be entered in the patient diary.

Patients will be asked to self-assess blood glucose levels at least 3 times a week from the run-in Visit (Visit 2) to Week 26.

Patients will be requested to self-assess blood glucose levels in the fasted state and whenever they experience any illnesses (eg, cold, flu), or symptoms of hyperglycemia or hypoglycemia. Symptoms of hypoglycemia may include shakiness, dizziness, sweating, hunger, headache, pale skin color, sudden moodiness or behavior changes (such as crying for no apparent reason), clumsy or jerky movements, seizure, difficulty paying attention or confusion, or tingling sensations

around the mouth. Patients will be instructed to record the presence of absence of hypoglycemic episodes or hypoglycemic symptoms in the patient diary provided.

Patients will also be instructed to record SMBG values that are  $\leq 70$  mg/dL ( $\leq 3.9$  mmol/L) in the patient diary. Patients should be instructed to contact the site if fasting SMBG values over 3 consecutive days are:

- $>270$  mg/dL (15.0 mmol/L) from Randomization up through the scheduled Week 8 visit
- $>240$  mg/dL (13.3 mmol/L) after the Week 8 visit up through the scheduled Week 12 visit
- $>200$  mg/dL (11.1 mmol/L) after the Week 12 visit and through the end of the 26-week double-blind Treatment Period

#### **9.2.1.7 Diabetic ketoacidosis**

Patients will be provided with instructions on how to recognize the symptoms of DKA and instructed to contact the site (or seek emergency medical services if after business hours) if these symptoms develop. Patients should have a full clinical evaluation with laboratory testing for possible DKA by the Investigator or emergency medical services physician. If such evaluation and laboratory testing confirm the presence of metabolic acidosis, then appropriate treatment should be implemented and the “Possible DKA” e-CRF should be completed. See [Appendix C](#) for further details.

### **9.3 OTHER ENDPOINTS**

#### **9.3.1 Pharmacokinetics**

The PK endpoint is:

- Plasma concentrations of sotagliflozin and its metabolite pre-dose at Weeks 4, 18 and 26 and 2 hours 30 minutes post-dose at Week 26

##### **9.3.1.1 Sampling time**

At Weeks 4 and 18 (Visits 5 and 8, respectively), blood samples for PK assessment are to be drawn with the other laboratory assessments. At Week 26, PK samples should be drawn at pre-dose and at 2 hours 30 minutes postdose, immediately after the respective glucose assessments during the MMTT. Pharmacokinetic samples (with the exception of the 2 hours 30 minute sample during the Week 26 MMTT) **must** be collected before administration of IMP. See [Table 3](#) for the identification of samples.

**Table 3 – Samples identification**

Visit	Week	Relative to dosing	PK
Visit 5	Week 4	Pre-dose	P00
Visit 8	Week 18	Pre-dose	P01

Visit	Week	Relative to dosing	PK
Visit 9	Week 26	Pre-dose	P02
Visit 9	Week 26	Post-dose 2 h 30 min	P03

## PK: pharmacokinetic

### 9.3.1.2 Pharmacokinetics handling procedure

Detailed procedures for sample preparation, storage and shipment are described in the specific laboratory manual.

### 9.3.1.3 *Bioanalytical method*

## Concentration of sotagliflozin and its 3-O-glucuronide

Plasma samples will be analyzed at Covance US using a validated high performance liquid chromatography-tandem mass spectrometry for sotagliflozin with lower limit of quantification of 2 ng/mL and for sotagliflozin-3-O-glucuronide with a lower limit of quantification of 10 ng/mL.

A series of horizontal black bars of varying lengths, likely representing redacted text or a visual representation of data. The bars are arranged vertically and have irregular, stepped ends, suggesting a digital or processed image of a document.

The image consists of six horizontal bars of varying lengths, rendered in black on a white background. The bars are positioned in a descending staircase pattern from the top left to the bottom right. The first bar is the longest and ends with a small black square. The second bar is shorter and ends with a small black square. The third bar is the shortest and ends with a small black square. The fourth bar is the longest and ends with a small black square. The fifth bar is shorter and ends with a small black square. The sixth bar is the shortest and ends with a small black square. The bars are separated by white space.

## 9.6 APPROPRIATENESS OF MEASUREMENTS

Sotagliflozin monotherapy in patients with T2D who have inadequate glycemic control with diet and exercise is expected to lower HbA1c over 26 weeks of treatment (primary efficacy analysis).

The concentration of HbA1c reflects the glycemic history of the previous 120 days and is thus an index of mean glycemia, documenting glycemic control over the past 2 to 3 months. Hemoglobin A1c has also been shown to correlate with the development of long-term complications of diabetes, and reduction of HbA1c is known to reduce the risk of long-term microvascular complications. Therefore, HbA1c is considered an appropriate primary endpoint for assessing the effect of a treatment on glycemic control. The duration of study treatment (26 weeks for the primary HbA1c endpoint) is considered to be sufficient for achieving stable conditions with IMP and for enabling an adequate assessment of time-dependent changes in HbA1c.

The problem of weight gain in T2D is widely recognized. More than 80% of individuals with T2D are overweight, many at the time of diagnosis. Consequently, iatrogenic weight gain is not only unwelcome, but represents an important clinical issue that can become a barrier to the successful management of glycemic control. Therefore, in this study assessing change in body weight from Baseline to Week 26 is a secondary endpoint.

Improvements in FPG and PPG have been observed with sotagliflozin in multiple studies. Therefore assessment of both fasting and post-prandial glucose (after a MM) is relevant in this study. These 2 parameters are also considered by regulatory agencies to be supportive of efficacy of an antidiabetic agent.

Phase 2 data indicated that sotagliflozin may reduce SBP by 10 to 15 mmHg in patients with SBP  $\geq$ 130 mmHg at baseline, while having no significant effect in patients with SBP <130 mmHg, and did not induce hypotension. Since this could be of benefit to patients with T2D, this finding is being followed up as a secondary objective in this trial, as well as the potential in patients with DBP >80 mmHg. Although effects on BP in Phase 2 data were observed with the 400 mg dose at 12 weeks, the effects will be examined at Weeks 12 and 26.

Endpoints for evaluating renal function include eGFR, based on serum creatinine, and urine albumin to creatinine ratio as well as routine monitoring of urine via dipstick and microscopy. UGE and urine GCR are other valid markers of renal function, and will be assessed at appropriate time points in this study.

Due to potential effects on bone and calcium metabolism, specific biomarkers for bone and calcium metabolism will be assessed at regular time points. In view of the SGLT1 inhibitory effects in the GI tract, specific markers of intestinal transit and absorption will also be measured.

The other efficacy and safety assessments in this study are standard, well-established measurements for a Phase 3 study evaluating the treatment of T2D in adult participants.

The length of the study is considered appropriate for detection of the primary endpoint given the power estimates (see [Section 11](#)).

## 10 STUDY PROCEDURES

### 10.1 VISIT SCHEDULE

The visit schedule and procedures/assessments are listed in the “Study Flow Chart” ([Section 1.2](#)). The aim of this section is to provide details on how some of the procedures/assessments should be performed.

This is an out-patient study and consists of 10 on-site visits, although optional on-site and/or telephone visits can be scheduled at any time for any reason during the study whenever considered necessary by the Investigator.

The patients need to be fasting for on-site visits V1 through V9 (Week -4 through Week 26), unless instructed otherwise by the Investigator. Throughout the study, “fasting” is defined as 8 hours without food. **Note:** If the patient is not fasting at the visits specified above, the blood sample will not be collected and a new appointment should be given to the patient for the following day if possible, with instruction to be fasted.

The Run-in visit can be performed as soon as the results of all screening tests are available and the patient is confirmed to be eligible for participation in the study. The visit window for visits V4 through V10 should occur within  $\pm 3$  days. If one visit date is changed, the next visit should occur according to the original schedule, ie calculated from the date of Baseline visit (Visit 3, Week 0).

For a complete list of procedures scheduled for each study visit please refer to the Study Flow Chart ([Section 1.2](#)), which details the procedures to be performed.

All data obtained during the trial visits will be reviewed by the Investigator and sub-investigators who are qualified in treatment of T2D and are trained on the study.

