### **6.1.2 Double-blind treatment period (Week 0 to Week 26)**

Eligible patients will be randomized on Day 1 (Visit 3). In order to qualify for randomization, patients must demonstrate compliance during the single-blind placebo Run-in Phase based upon tablet count ( $\geq 80\%$ ).

Randomization will be stratified by:

Following randomization, patients will be treated in a double-blind manner for 26 weeks. All patients will have PPG assessed following a MMTT at Weeks 0 and 26. In the original version of this protocol, it was planned for a total of 240 patients  $\geq 18$  years of age (or  $\geq$  legal age of majority if greater) to be randomly assigned 1:1 to the following 2 treatment groups:

In the amended, current, version of this protocol, a total of 300 patients  $\geq 18$  years of age (or  $\geq$  legal age of majority if greater) will be randomly assigned 1:1:1 to the following 3 treatment groups:

- Sotagliflozin 200 mg as one 200 mg tablet and one placebo tablet (identical to sotagliflozin in appearance), once daily
- Sotagliflozin 400 mg as two 200 mg tablets, once daily
- Placebo as two placebo tablets (identical to sotagliflozin in appearance), once daily

The enrollment will be completed when each of the 3 treatment groups (placebo, sotagliflozin 200 mg, and sotagliflozin 400 mg) reaches approximately 100 patients.

Fasting glucose (plasma or serum), HbA1c, and PPG will be masked to study sites and patients after randomization until study end. To prevent partial unblinding, UGE and GCR results will be masked to study sites and patients, and the central laboratory urine dipstick will not include the measurement of urine glucose.

If a patient discontinues treatment with investigational medicinal product (IMP) early during the 26-week Treatment Period, the patient will have a Premature End-of-Treatment (EOT) Visit, and a Follow-up Visit 4 weeks after the last dose of IMP. In addition, every effort will be made to have all patients return to the site at the time corresponding to their scheduled visits, particularly the Week 26 Visit. If the patient does not agree to site visits, they will be contacted by telephone to inquire about safety status.

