#### 9.1.1 Primary efficacy endpoint

- Comparison of sotagliflozin 400 mg versus placebo in change from Baseline to Week 26 in HbA1c (%).

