#### **9.1.4.3 *Fasting plasma glucose measurement***

Plasma glucose is measured in the fasting state at Screening (Visit 1) and all on-site visits during the treatment period. For the eligibility and efficacy assessments of the study, FPG is measured at a central laboratory to allow estimation of change from Baseline to Week 26 in FPG.

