2.4.4.1 Analysis of primary efficacy endpoint(s)

The statistical tests will be two-sided tests at a nominal 5% significance level.

Primary analysis

The primary efficacy endpoint of change in HbA1c from baseline to Week 26 will be analyzed by an Analysis of Covariance (ANCOVA) model using HbA1c values measured at baseline and Week 26 (observed or imputed). The missing data at endpoint will be imputed by multiple imputation (MI) methods in 2 parts as detailed below. To be concise, the following texts related to imputation are generalized to accommodate primary as well as continuous secondary efficacy endpoints.

Statistical Analysis Plan

Version: 3

Lexicon Pharmaceuticals Protocol No. EFC14833

Date of Issue: 21-Nov-2019

Covance Study ID: 000000150524

Missing endpoint data at Week 26 (or Week 12 for SBP) visit will be imputed using a model built separately in each treatment group and estimated from the patients in the same treatment group who prematurely discontinue the IMP before the Week 26 (or Week 12 for SBP) visit but have the measurement for the endpoint (ie, retrieved dropouts). The imputation model will include the randomization strata and the corresponding baseline value. In cases of non-convergence during the imputations, the offending stratum will be identified and then will be dropped from the model. Considering that the number of retrieved dropout patients in each treatment group is expected to be small, a simple imputation model based on regression will be used with baseline measurement included as the predictor. This will serve as the primary method of imputation for missing data should sampling criteria be satisfied (see below).

An alternative (back-up) imputation method will be used if the number of patients who prematurely discontinue the IMP before the Week 26 (or Week 12 for SBP) visit but have the measurement for the endpoint is < 5 in any treatment groups (ie, an insufficient number of retrieved dropouts to support the imputation method described above). This criterion will be assessed for each primary or continuous secondary efficacy endpoint.

In the back-up imputation method, missing post-baseline endpoint values at Week 26 (or Week 12 for SBP) will be imputed by the washout Multiple Imputation (MI) method under the missing not at random (MNAR) framework.

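### Section 10.1 withholds all blood sampling from a non-fasting patient, HbA1c included, so a Week 26 primary-endpoint value can be missed in a patient who is on site

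*Protocol*

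**What the plan says.** Protocol section 10.1 sets the fasting rule: "The patients need to be fasting for on-site visits V1 through V9 (Week -4 through Week 26), unless instructed otherwise by the Investigator". The note that follows reads: "If the patient is not fasting at the visits specified above, the blood sample will not be collected". The same sentence offers a new appointment for the next day where that can be arranged. The note draws no distinction between tests, and neither the HbA1c method (section 9.1.4.1) nor the Week 26 visit list (section 10.1.2.1.2) adds an exception.

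The primary endpoint is measured at one of these visits: "Comparison of sotagliflozin 400 mg versus placebo in change from Baseline to Week 26 in HbA1c".

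Where a test depends on fasting, the protocol generally says so. Section 9.1.4.3 states: "Plasma glucose is measured in the fasting state at Screening (Visit 1) and all on-site visits during the treatment period". Section 9.1.4.2 requires fasting for the mixed meal test, and the visit lists specify fasting lipids. Section 9.1.4.1 states no such condition for HbA1c. Section 9.6 says: "The concentration of HbA1c reflects the glycemic history of the previous 120 days and is thus an index of mean glycemia".

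For patients who stop IMP early, section 6.1.2 asks sites to make every effort to "have all patients return to the site at the time corresponding to their scheduled visits, particularly the Week 26 Visit".

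SAP section 2.5.4 (Table 4) allows an unscheduled or premature end-of-treatment measurement to stand in for Week 26 if taken on study day 154 or later. If there is none, the value is missing. It is then multiply imputed (SAP 2.4.4.1), and the patient counts as a non-responder for both HbA1c thresholds (SAP 2.4.4.2).

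**The concern.** A site that follows the note literally sends home a patient who is present at Week 26 without taking the primary-endpoint sample, because of a condition that matters for other tests. If the patient does not come back, the trial has created its own missing value.

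The patients for whom this matters most are those who have stopped IMP and still attend Week 26. Under section 9.1.4.2 they have no mixed meal test at that visit, so there is less reason to insist on a fasting session. Their HbA1c is what the SAP's first-choice imputation is built on: the model is fitted, within each group, to patients who stopped IMP early but have the endpoint measured. If any group has fewer than five, the SAP switches to the washout method.

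The responder rule adds a second consequence. HbA1c <7.0% for 400 mg is a formal step in the fixed sequence (SAP 2.4.4.4) and stands immediately before the 200 mg tests.

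**Working it through.** **1. Does the rule reach the primary endpoint?** The note covers Visits 1 to 9, and Week 26 is Visit 9. It withholds the blood sample without exception. HbA1c is a blood test at that visit, so it does. That HbA1c needs no fasting is an inference from the silence of section 9.1.4.1 and the description in section 9.6; no sentence says it outright.

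**2. What has to happen for the value to be missing?** All of the following:
- the patient arrives non-fasting, and the investigator has not used the discretion in section 10.1;
- the patient does not return the next day or at another visit;
- no other HbA1c exists from study day 154 onward.

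Visit 10 (section 10.1.3.1) does not list HbA1c, so routine follow-up does not recover it.

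**3. How many values?** The documents give no rates. As assumptions, take 3–8% arriving non-fasting and 25–50% of those not returning, which is a loss of 0.75% to 4% per attendee. From the SAP's counts, 400 mg and its pooled placebo have about 76/2 + 300/3 = 138 patients each; 200 mg and its comparator have about 100 each.
- 138 per arm: 138 × 0.03 × 0.25 = 1.0 to 138 × 0.08 × 0.50 = 5.5.
- 100 per arm: 0.75 to 4.0.

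**4. Power.** Formula: Φ(δ / (σ√(2/n)) − 1.96), with σ = 1.2.
- Plan's figure for 400 mg (n = 100, δ = 0.6): Φ(3.536 − 1.960) = 94.2%; stated 94%.
- Plan's figure for 200 mg (n = 100, δ = 0.5): Φ(2.946 − 1.960) = 83.8%; stated 84%.

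Both are reproduced. For a fraction m lost, the higher figure below cuts n to n(1 − m). The lower figure also cuts δ to δ(1 − m), as a rough stand-in for placebo-based imputation.

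| Comparison | m = 0 | 1% | 2% | 5% |
|---|---|---|---|---|
| 400 mg, 138 per arm | 98.6% | 98.5–98.4% | 98.4–98.1% | 98.2–97.0% |
| 400 mg, 100 per arm | 94.2% | 94.0–93.6% | 93.8–92.9% | 93.1–90.6% |
| 200 mg, 100 per arm | 83.8% | 83.4–82.7% | 83.1–81.6% | 81.9–77.9% |

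At 1–2% loss the largest fall is about 2.3 points (200 mg, 83.8% to 81.6% before rounding).

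**5. Responder proportions.** Each missing value lowers an arm's proportion by at most 1/138 = 0.7 points. At 5.5 losses the ceiling is 5.5/138 = 4.0 points, reached only if every one of those patients would have responded.

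**6. The five-patient threshold.** Apply the same 0.75–4% to patients off IMP who attend.
- Exactly 5 in a group: chance of losing at least one is 1 − 0.9925⁵ = 3.7% to 1 − 0.96⁵ = 18.5%.
- Exactly 6: chance of losing at least two is about 0.1% to 2.2%.

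The documents give neither the number of such patients nor a separate non-return rate for them.

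**The case against.** The strongest reply is that the loss needs a chain of events, each with an answer in the documents. Next-day rebooking is in the same sentence and normally falls inside the ±3-day window. Section 10.1 permits optional visits at any time and lets the investigator vary the fasting instruction. The SAP's Week 26 window has no upper limit, so even an unscheduled draw at the Week 30 visit would count. The washout fallback is prespecified, and it is reported as a sensitivity analysis when the retrieved-dropout method is primary. Keeping all samples in one fasting session is also a reasonable choice: a patient already sampled for HbA1c has less reason to return for FPG and the mixed meal test, which lead the secondary sequence.

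Most of this stands and limits the point. It does not remove it: none of these provisions tells a site to take HbA1c from the patient in front of it, and the recovery routes work only if someone orders a draw that the note discourages.

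A reader might go further and infer three things that the documents do not support:
- **That every non-fasting Week 26 arrival loses the endpoint, or that power is threatened.** Rebooking and the open window make the loss conditional, and the power figures barely move.
- **That the rule will push a group below five retrieved dropouts.** This requires a group to sit at the threshold already, and no document says that one does.
- **That everything except FPG, lipids and the meal test can be drawn non-fasting.** The chemistry panel contains serum glucose (protocol Table 2), which SAP section 2.1.4.4 presents as an efficacy parameter. Chemistry is in any case repeated at Visit 10.

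**Conclusion.** The point holds in a limited form. As written, section 10.1 can leave the Week 26 HbA1c unmeasured in a patient who is on site, for a reason the protocol does not attach to HbA1c. The result is avoidable missing data on the primary endpoint and avoidable non-responder coding. The expected number is probably small: about 1 to 6 per arm at 138 per arm, on assumed rates that the documents neither support nor contradict. The effect on power is minor, and a change of imputation method is possible but not shown to be likely. The change is worth making because it is nearly free, not because the trial's conclusion is at risk.

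**What to change.** Amend the note in section 10.1 and repeat it in section 10.1.2.1.2, along these lines: at post-randomization visits where HbA1c is scheduled, above all Week 26, the HbA1c sample is drawn at the attended visit whatever the patient's fasting status. The fasting-dependent samples are still rebooked for the next day: FPG, fasting lipids, the chemistry panel because it includes serum glucose, and the mixed meal test with its linked samples where it applies. Carry the same wording into the laboratory manual.

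The cost is a second venepuncture for patients who return. There may also be slightly less incentive to return for FPG and the mixed meal test, so the rebooking instruction should stay mandatory. No endpoint, test or sample size changes.
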